## List of Appendices

**Appendix 1. Questionnaire for telephonic survey.**

**Appendix 2. Medical questionnaire.**

**Appendix 3. SARS-CoV-2 antibody test results.**

**Appendix 4. Participant Information Sheet and Informed Consent Form.**

## **1. Introduction**

Population analysis of infection spreading is one of the key methods of new epidemics control. The World Health Organization has included population serological surveys, which help to visualize the new virus distribution, into a list of essential assessments during the current epidemics, along with the vaccine development and search for effective treatments for severe disease. Such studies help understand real disease spread and a real proportion of fatal outcomes among the patients with a disease and infected persons. Initial studies have shown the presence of immune response to an earlier SARS-CoV-2 infection.

Regarding the SARS-CoV-2 pandemic, the population assessment of immune response is recommended until the year 2024, as currently there is a discussion of a high risk of second and further peaks of new coronavirus epidemics. Initial studies performed in the state of New York have shown that up to 14% state residents and 21.2% of New York City residents had had the infection and had developed antibodies. In the states of Idaho and California, there were not more than 2% of such people.

To evaluate the proportion of people who have had the disease in a whole population (a city, a region, a country), the representativeness of a sample needs a strict approach. The methodology of a serological study is in many aspects similar to a sociological survey but is more complicated due to the use of serological test results. In addition, the population characteristics of these tests, i.e. sensitivity and specificity, are not always well-known. A serological study sample should be representative for the general population (age groups, gender, place of living, mobility during the epidemics).

In Russia, several studies have been performed to evaluate the proportion of antiviral antibody carriers, but many studies are probably biased in the direction of overestimation of positive results. This is caused by the selection of participants with higher probability of having antibodies. Thus, it is difficult to estimate how well these results reflect the real infection spread. In addition, such a study may help to identify objective social patterns of the epidemic spread in each specific region, i.e. correlation with the age, gender, occupation, mobility, and other factors. Also, some regions of Russia may have different stages of the epidemics, due to a geographical pattern of the viral spread. For example, in the Far East, there is high probability of viral spread from China, and in the European part of Russia from Europe.

Several designs exist to conduct blood antibody testing with the aim of studying the distribution of an infection. To evaluate a proportion of people who have had the infection up to the current moment, it is enough to assess the results of the tests performed in a representative sample in a short period of time. To evaluate the dynamics of the infection spread, similar testing in similar samples should be performed repeatedly, with specific time intervals at least of 4 weeks. There is also an option of a cohort study to evaluate the results of repetitive tests in the same sample defined at baseline. The latter design permits to define how the number of infected people in the population changes in time, evaluate the individual immune dynamics, and identify not only the distribution but also incidence of the infection.

## **2. Study objectives**

### **2.1.Primary objective**

**Pilot study:** to evaluate the proportion of people in St. Petersburg, Russia who have had the SARS-CoV-2 infection by means of analyzing the results of the blood serum tests for antiviral antibodies.

**Cohort study:** to evaluate the dynamics of the SARS-CoV-2 infection spread (incidence) by means of analyzing the results of blood serum tests for antiviral antibodies.

## 2.2.Secondary objectives

- To evaluate the incidence in the cohort study.
- To evaluate the relation between the risk of infection and several factors (mobility, social characteristics).
- To evaluate individual immune dynamics (seroconversion, seroreversion).
- To compare the proportion of participants with positive test results between age (<20, 20-29, 30-39, 40-49, 50-59, 60-69, >70) and gender groups.

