#### **3.2.2. Study exclusion criteria:**

- 3.2.2.1. Refusal to take part in any of the study surveys.
- 3.2.2.2. Impossibility to perform an anti-SARS-CoV-2 antibody test.
- 3.2.2.3. Signs or symptoms of an acute respiratory infection at the moment of a survey or a test, based on the information provided by the participant or on the results of an examination at the investigational site. (The symptoms of an acute respiratory infection may include fever, cough, runny nose, loss of olfaction, marked weakness, dyspnea. A final decision on the presence or absence of the symptoms will be taken on the basis of analysis of observed and medical data).
- 3.2.2.4. Participants younger than 18 years old cannot take part in this study.
- 3.2.2.5. Residence in distant district of the city (Kronshdatsky, Kurortny, Petrodvortsovy, Krasnoselsky, Kolpinsky, Pushkinsky)

Participation in the study is not limited by a single blood draw and anti-SARS-CoV-2 antibody test. The consent to the information transfer maintains for similar repetitive tests and other medical information necessary in the frame of this study.

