#### **5. Statistical analysis**

##### **5.1. Sample**

In this study, a population of a region with the size of  $N$  is being looked at. Assuming that the number of infected ( $K$ ) in the population is distributed binomially and the serological test is ideal, 2-sided 95% Wilson confidence interval for the prevalence ( $p$ ) is:

$p' \pm z_{0,025} \sqrt{\frac{p'(1-p')}{n+4}}$ , where  $p' \equiv \frac{k+2}{n+4}$ , and  $z_{0,025}$  is the critical level of the standard normal distribution. In this case the sample size  $n$ , needed for the sample error to not exceed  $M$ , with a conservative assumption of hypothetical prevalence of 50%, is:  $n > \left(\frac{1,96 \times 0,5}{M}\right)^2 - 4$ . For the sample error to reach 2%, at least 2397 observations are needed.

If we assume that hypothetical prevalence is 10%, the sample size is less than 900 for the sample error of 2%. Taking into account possible attrition at the repetitive tests, it is planned to enroll at least 1000 participants.

During the study, it is planned to test at least 1000 participants with a highly sensitive (Se) and highly specific (Sp) test, to reach the sample error level of 2%. The calculations above are applicable to a cross-sectional study. In a cohort study, there is a problem of the sample attrition. We assume loss of 5% of participants at the repetitive blood sampling. If 1000 participants provide samples at the first visit, there will be 630 tested participants at Week 36.

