### 5.3.1. Primary objective

**Cross-sectional study:** the main objective of this study is to calculate the proportion of participants with the presence of antibodies (taking into account the threshold recommended by manufacturer) in the total number of tested. Crude value will be equal to the proportion of positive-tested persons in the total number of enrolled. Additionally, standardized values and values in age or gender groups will be calculated as well as an adjusted value based on the total population in a region.

**Cohort study:** the main objective of the cohort study is to compare correspondent values of prevalence in different points in time. This comparison will be made using simple tests and models depending on the type of value (rough, standardized, adjusted).

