### CLARIFICATIONS FOR AN INTERVIEWER:

What does the test show: it's a test for antibodies. It shows if you have had a coronavirus infection earlier (as this infection is often asymptomatic or similar to other diseases). It does not show if you are currently infected. It is free of charge.

Results of the test will not be reported to state organizations.

What are Scandinavia clinics: it's the largest private clinics chain in St. Petersburg, one of the centers of urgent medical care in case of coronavirus infection.

Q1001 Single choice from 'Q1001 list'

We guarantee that your answers will be kept confidential. For the quality control of my work, this call will be recorded, and the record will be deleted after the end of the study. Do you agree to proceed to a survey?

How can I refer to you?

informationText('Respondent name: ' + Q.openValueTxt);

Q1

Sex

(DON'T READ THE QUESTION, REGISTER THE ANSWER BASED ON EARLIER ANSWERS)

Single choice from 'Q1 list'

1 Male

2 Female

Q2

Please tell me, do you live in St. Petersburg?

(DON'T READ ANSWERS)

(A SINGLE ANSWER) Single choice from 'Q2 list'

1 Yes

2 No

If Q2=2, terminate the interview

Q3 Single choice from 'Q3 list'

In which district of St. Petersburg do you live?

(DON'T READ ANSWERS)

(A SINGLE ANSWER)

1 admiraltEiskiy

2 vasileostrOvskiy

3	vYborgskiy	
4	kAlininskiy	
5	kIrovskiy	
6	kOlpskiy	
7	krasnogvardEiskiy	
8	Krasnoselskiy	
9	KronshtAdtskiy (KronshtAdt)	
10	Kurortniy	
11	Lomonosovskiy	
12	Moskovskiy	
13	Nevskiy	
14	PetrogrAdskiy	
15	PetrodvortsOviy	
16	primOrskiy	
17	pUshkinskiy	
18	frUnzenskiy	
19	Centralniy	
998	OTHER (explain)	OpenValueTxt

Q4     Numeric

How old are you in full years?

If Q4(ValueInt<18), terminate the interview

Q5     Single choice from 'Q5 list'

Please tell me if since the beginning of February, you have been to somewhere outside of St. Petersburg and Leningrad region?

(DON'T READ ANSWERS)

(A SINGLE ANSWER)

1       Yes

2       No

Q6     Single choice from 'Q6 list'

Q5=1

Have you traveled abroad since the beginning of February?

1       Yes

2       No

Q7     Single choice from 'Q7 list'

Among the people who you have met after the 1st of March, are there people who have traveled abroad in February or later?

(DON'T READ ANSWERS)

(A SINGLE ANSWER)

1       Yes

2       No

999            (DON'T READ) Not sure

Q8

Have you exited your home during the last week (7 days)?

(DON'T READ ANSWERS)

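### The age bands in Section 2.2 leave participants aged exactly 70 in no group, and the under-20 band can hold only 18- and 19-year-olds and will be sparse

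*Protocol*

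**What the plan says.** Protocol Section 2.2 lists as a secondary objective a comparison of positive results between gender groups and between groups by "age (<20, 20-29, 30-39, 40-49, 50-59, 60-69, >70". The cut-points are printed inside the objective, and no other section defines age groups.

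Three other places bear on how the bands work:

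- Section 3.2.2, exclusion criterion 3.2.2.4: "Participants younger than 18 years old cannot take part in this study". The telephone questionnaire in Appendix 1 enforces this: "If Q4(ValueInt<18), terminate the interview".
- The age question in Appendix 1 takes a numeric answer and asks "How old are you in full years".
- Section 5.3.1, on the cross-sectional primary objective, adds that "standardized values and values in age or gender groups will be calculated". It names no bands and does not refer back to Section 2.2.

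**The concern.** Prespecified cut-points should place every eligible person in exactly one group. Here the second-to-last band ends at 69 and the last begins above 70. With age held as a whole number, 70 is an ordinary recorded value, so the gap covers a full year of age. An analyst who codes the bands as printed loses those participants from the comparison. One who corrects the boundary departs from the protocol text without saying so.

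At the other end, the eligibility limit cuts the under-20 band to two years of age. Its estimate will be much less precise than those of the ten-year bands, and contrasts that involve it will say little.

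What is at stake is the completeness and readability of one secondary comparison. If Section 5.3.1 uses the same bands, its age-specific values share the problem, and so would any age standardisation built on them.

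**Working it through.** **Inputs from the protocol**

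- Bands: Section 2.2.
- Lower age limit of 18: Section 3.2.2 and Appendix 1.
- Age in completed years: Appendix 1.
- Enrolment, Section 5.1: "it is planned to enroll at least 1000 participants".
- Prevalence of 10%, one of the two sizing assumptions in Section 5.1.
- Retention, Section 5.1: "If 1000 participants provide samples at the first visit, there will be 630 tested participants at Week 36".

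**The plan's own figures**

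The protocol gives no expected number per band, so its sizing figures are reproduced first to confirm the inputs.

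- 50% prevalence, 2% error: (1.96 × 0.5 / 0.02)² − 4 = 2401 − 4 = 2397, as stated.
- 10% prevalence, 2% error: 1.96² × 0.09 / 0.02² − 4 = 864.4 − 4 = 860.4, consistent with the stated bound of 900.
- Week 36: 1000 × 0.95⁹ = 630.2, stated as 630.

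None of these depends on the age bands.

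**Band check**

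Each whole age from 18 to 100 was assigned to the printed bands. Age 70 is the only one with no band. No age falls in two bands. The under-20 band contains 18 and 19 only.

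**Number aged exactly 70 (assumed age distribution)**

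Assume 1000 participants spread uniformly from 18 to an upper age U. The count at any single age is 1000 / (U − 17).

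- U = 74: 1000 / 57 = 17.5
- U = 80: 1000 / 63 = 15.9
- U = 90: 1000 / 73 = 13.7

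This gives about 14 to 18 people, or 1.4% to 1.8%.

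**Number aged 18-19 (assumed share)**

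Uniform ages with U from 80 to 90 give 2000 / 63 = 31.7 down to 2000 / 73 = 27.4. A real sample could hold fewer, so a share of 1% to 3.5% is assumed, which is 10 to 35 people with 1 to 3.5 expected positives at 10% prevalence.

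The Wilson score interval is [p + z²/2n ± z√(p(1−p)/n + z²/4n²)] / (1 + z²/n), with p = 0.10 and z = 1.96:

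- n = 10: (0.2921 ± 0.2673) / 1.3842 = 1.8% to 40.4%
- n = 35: (0.1549 ± 0.1135) / 1.1098 = 3.7% to 24.2%

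If the comparison were repeated at Week 36, 630 × 0.01 to 630 × 0.035 leaves about 6 to 22 people. Section 2.2 does not tie the comparison to that visit.

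**Effect of merging the first two bands**

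Take uniform ages 18-79, which is 62 years at 1000 / 62 = 16.1 per year. The 18-19 band holds 2 × 16.1 = 32 people. With 3 of 32 positive, the Wilson interval is 3.2% to 24.2%. An 18-29 band holds 12 × 16.1 = 194, or about 190. With 19 of 190 positive, the interval is 6.5% to 15.1%.

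**The case against.** The sequence of ten-year bands makes the intended last group obvious, and most analysts would code it as 70 and over. The printed symbol may be a drafting slip, or a greater-or-equal sign altered in translation or when the PDF was read. The text cannot settle which. If it is only a reading artefact, the age-70 half of the point falls. Age is stored as a number, so no data are lost, and boundary coding is often left to an analysis plan. This stands as a reason to rate the point low. It does not remove the point, because the protocol did not leave the grouping open: it printed cut-points, and as printed they miss one year of age.

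The under-20 label is not an error either. Every eligible person under 20 is classified once, and nothing conflicts with the 18-year limit. This objection stands in full. The case for merging rests on precision alone.

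A reader might go further and call the first band near-empty or too small to estimate. The documents do not support that. They give no age distribution, and the assumed range of 10 to 35 people yields wide intervals, but intervals all the same. A reader might also infer that the age-standardised prevalence in Section 5.3.1 omits a year of age. That section names no bands, so the link is an inference.

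**Conclusion.** The point holds as a minor defect. As printed, participants aged exactly 70 fall in no group of the age comparison, and the under-20 group is a sparse two-year band.

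The size rests on assumptions, since the protocol gives no age distribution: about 14 to 18 of 1000 aged 70 if ages are uniform, and 10 to 35 aged 18-19 if their share is 1% to 3.5%. The unassigned age follows from the text alone, provided the last band is printed as the sponsor wrote it.

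It would be wrong to infer that people aged 70 are excluded from the study or that the main estimate is biased. No section excludes them. Crude prevalence, the selection-corrected prevalence in Section 5.3, and the incidence and seroconversion measures in Section 5.3.2 do not use these bands as written. The effect is confined to the secondary age comparison and, only if the bands are shared, to the age-specific and standardised values in Section 5.3.1.

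**What to change.** In Section 2.2, write the last band as 70 and over. Preferably merge the first two bands into 18-29, so that the groups are 18-29, 30-39, 40-49, 50-59, 60-69, and 70 and over. If a separate youngest group is wanted, label it 18-19 and accept that it will be imprecise. State in Section 5.3.1 that the age-specific and standardised values use the same bands.

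The cost is a line or two of text. No sample-size figure, data item or visit changes. Merging gives up a separate estimate for ages 18-19, which would be imprecise in any case.

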## 3. Study procedures

### 3.1.Study design

This non-interventional observational socioepidemiological population study will be conducted in residents of St. Petersburg, Russia. Selection and invitation of participants will take place during telephonic survey. After giving signed informed consent, each participant will be subjected to a blood test for SARS-CoV-2 antibodies and will answer a questionnaire. The testing will be performed primarily using serological assays for serum IgG approved in the Russian Federation (Abbott Architect IgG and Genetico).

This study involves a telephonic sociological survey during which respondents will be invited to undergo a blood test for SARS-CoV-2 antibodies at the participating investigational sites in different cities and towns of Russia. The participants will undergo such a test, take part in an additional survey for those who plans or have already done such a test, and receive the results. A part of participants will be offered to use a taxi (see Section 5.2). Testing and questionnaire at the clinic will be repeated several times. It is planned to perform up to 10 visits which will include blood sampling, testing, and collection of additional information.

**Table. Calculation of the study sample taking into account approximately 5% attrition at each visit**

	First visit	Week 4	Week 8	Week 12	Week 16	Week 20	Week 24	Week 28	Week 32	Week 36
Telephone-based questionnaire; medical hypothesis; IgG tests	1000	950	902	857	815	774	735	698	663	630

Study participants will be asked to undergo multiple tests for SARS-CoV-2 antibodies with 4-week intervals to assess the immune response dynamics. If a participant agrees to repetitive tests, they will also complete questionnaires with the objective of collecting epidemiological information for the period since the first test. Time of each round of survey and information collection will not exceed 4 weeks.

If the test is not performed in the mentioned interval, delayed testing data may be used. If before the initial or a later test a participant shows signs of acute respiratory infection (see Section 3.2.2.3) or has been diagnosed with COVID-19, the study will use results of

a test performed at least 2 days after all symptoms resolved, or results of the last negative test for the virus.

### **3.2. Inclusion and exclusion criteria**

#### **3.2.1. Study inclusion criteria:**

- 3.2.1.1. Residence in St. Petersburg, Russia.
- 3.2.1.2. Consent to participate in a telephonic survey and personal data collection.
- 3.2.1.3. Consent to an anti-SARS-CoV-2 antibodies test at an investigational site, and to management of the results of such a test with scientific objectives.
- 3.2.1.4. Consent to second and further surveys and tests with approximately 4-week intervals.

The participation in surveys and information collection should be based on a verbal (for telephonic surveys) and written (for surveys and information transfer from a clinic) informed consent. The participants will sign 2 copies of the informed consent form, one of which will be given to a participant, and another will stay at the investigational site. The participants will be also asked to agree to the transfer of additional medical data available at the clinic, for scientific analysis. The refusal to provide additional medical data is not an exclusion criterion.

#### **3.2.2. Study exclusion criteria:**

- 3.2.2.1. Refusal to take part in any of the study surveys.
- 3.2.2.2. Impossibility to perform an anti-SARS-CoV-2 antibody test.
- 3.2.2.3. Signs or symptoms of an acute respiratory infection at the moment of a survey or a test, based on the information provided by the participant or on the results of an examination at the investigational site. (The symptoms of an acute respiratory infection may include fever, cough, runny nose, loss of olfaction, marked weakness, dyspnea. A final decision on the presence or absence of the symptoms will be taken on the basis of analysis of observed and medical data).
- 3.2.2.4. Participants younger than 18 years old cannot take part in this study.
- 3.2.2.5. Residence in distant district of the city (Kronshdatsky, Kurortny, Petrodvortsovy, Krasnoselsky, Kolpinsky, Pushkinsky)

Participation in the study is not limited by a single blood draw and anti-SARS-CoV-2 antibody test. The consent to the information transfer maintains for similar repetitive tests and other medical information necessary in the frame of this study.

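### Prevalence is claimed for all of St. Petersburg, but minors and six districts are excluded, the printed telephone script does not screen on district, and repeat-test consent is required in one place and conditional in another

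*Protocol*

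**What the plan says.** **Target.** Protocol Section 2.1 sets the pilot objective as "to evaluate the proportion of people in St. Petersburg, Russia who have had the SARS-CoV-2 infection". Section 3.1 says the study "will be conducted in residents of St. Petersburg, Russia", and inclusion criterion 3.2.1.1 asks only for "Residence in St. Petersburg, Russia". Section 5.3.1 adds standardised values "as well as an adjusted value based on the total population in a region".

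**Exclusions.** Criterion 3.2.2.4 removes everyone under 18. Criterion 3.2.2.5 removes people by "Residence in distant district of the city (Kronshdatsky, Kurortny, Petrodvortsovy, Krasnoselsky, Kolpinsky, Pushkinsky".

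**Telephone script (Appendix 1).** Q2 ends the interview for people living outside the city, and Q4 ends it for those under 18. Between them, Q3 asks "In which district of St. Petersburg do you live". Its answer list contains all six excluded districts, and no stop follows it. The offer of free testing at Q36 shows no condition on Q3 and does not mention repeat tests.

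**Analysis.** Section 5.2 treats non-participation as a choice made by the person surveyed. Section 5.3 lists a single imputation for people without a result and corrections for observed and unobserved self-selection.

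**Repeat tests.** Criterion 3.2.1.4 requires "Consent to second and further surveys and tests with approximately 4-week intervals". Section 3.1, below the attrition table, says "If a participant agrees to repetitive tests, they will also complete questionnaires".

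**The concern.** The population named in the objective is wider than the population that can supply a blood sample. No weighting or modelling can draw on test results from a district, or an age group, in which nobody is eligible. The Introduction itself lists age and place of living among the features on which a serological sample should be representative, and the exclusions act on both.

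The script raises a second question. A resident of an excluded district can complete the interview, hear the offer and have no result because of ineligibility rather than refusal. The planned corrections are built to explain refusal. If the two kinds of untested person are pooled, participation looks lower than it was, and the imputed and model-based prevalence can be distorted.

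Third, cross-sectional prevalence needs one sample per person. Read literally, 3.2.1.4 turns away people willing to give that sample who say in advance that they will not return. That adds self-selection to the estimate that Section 5.2 tries to protect.

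**Working it through.** **1. The plan's own precision figures (Section 5.1).** At 50% prevalence and a 2-point error, n = (1.96 × 0.5 / 0.02)² − 4 = 2401 − 4 = 2397, as stated. At 10% prevalence, 1.96² × 0.1 × 0.9 / 0.02² = 864; solving with the protocol's own interval gives 875. Both are below 900, as stated. With n = 1000 and 10% prevalence the half-width is 1.87 points. The arithmetic is sound, but it measures sampling error only and makes no allowance for coverage.

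**2. Coverage bias for the city.** Let w be the share of the population living in the six districts, and p_in and p_out the prevalence inside and outside the sampled area. The city value is (1 − w) × p_in + w × p_out. Reporting p_in as the city value is wrong by

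bias = p_in − [(1 − w) × p_in + w × p_out] = w × (p_in − p_out).

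The protocol gives neither w nor p_out. Assuming w of 10-30% and a gap of 5 points in either direction:

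| w (assumed) | Bias for a 5-point gap | Gap at which bias equals 2 points (2 / w) |
|---|---|---|
| 10% | 0.1 × 5 = 0.5 points | 20 points |
| 20% | 0.2 × 5 = 1.0 point | 10 points |
| 30% | 0.3 × 5 = 1.5 points | 6.7 points |

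The same formula applies to minors, with their population share as w. That share is not given either, and no figure is attempted.

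**3. The script against the criteria.** The six excluded districts are Q3 codes 6, 8, 9, 10, 15 and 17, out of 19 named districts. The two other screening questions, Q2 and Q4, have printed stops; Q3 has none. As printed, a respondent with any of these codes reaches Q36 and receives the offer.

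**4. Effect on apparent participation.** If ineligible people make up a share w of those surveyed and none is tested, any participation rate is multiplied by (1 − w). With w = 20% and 20% participation among the eligible (both assumed), 0.20 × 0.8 = 16%. The imputation would also supply results for people in districts with no tested person to learn from, and the selection models would try to explain as choice what is a rule. How far prevalence then moves depends on the covariates and the model, and cannot be computed from the protocol.

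**5. Effect on the taxi comparison.** The offer is randomised, so ineligible people are balanced between the groups and add no tests and no positives to either. Both the difference in positives and the difference in tests shrink by (1 − w), so their ratio, the prevalence among people swayed by the offer, does not change. Strength barely moves. For illustration, assume 5000 eligible people per group with 20% and 25% tested:
- Eligible only: 250 / √(5000 × 0.20 × 0.80 + 5000 × 0.25 × 0.75) = 250 / √(800 + 937.5) = 6.0.
- With 20% ineligible (6250 per group, 16% and 20% tested): 250 / √(840 + 1000) = 5.8.

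**6. Repeat consent.** Criterion 3.2.1.4 concerns consent, not attendance. Someone who consents and comes once is a valid first-visit observation, and Section 5.1 plans for 5% loss at each repeat. Only people who decline repeats in advance are shut out, and Section 3.1 suggests that even they may be tested once.

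**The case against.** The strongest reply is that nothing says ineligible respondents stay in the models. District is recorded at Q3, so the exclusion can be applied at analysis, and the definition of analysis sets is commonly left to a statistical analysis plan, which is not at hand. The printed script is also visibly incomplete: it calls a question, Q8001, that is not shown. The clinic phones each person to book and could screen on district then.

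Much of this stands. A reader might infer that people who could not take part will be modelled as refusers; the protocol does not settle that, so the point is conditional. Calling these people non-participants does not settle it either. Anyone who declines the test also fails 3.2.1.3, so the term used in Section 5.3 for those without a result must already reach beyond people who meet every criterion. A screen at the booking call, which no section describes, would still leave them among the surveyed.

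A reader might also infer that the taxi offer loses its power to identify the correction, because a 5-point effect would become 5 × 0.8 = 4 points. Step 5 shows this is mainly a change of scale. Nor are people who attend only once barred, as step 6 shows.

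Two further replies are fair. The region in Section 5.3.1 is not defined, so that sentence alone does not prove adjustment to the excluded districts; the city-wide claim rests on Sections 2.1, 3.1 and 3.2.1.1. And every size in step 2 rests on assumed inputs and stays below 2 points in the range shown. The 2-point error is, however, a sampling margin, and a coverage bias comes on top of it.

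**Conclusion.** The mismatch between target and sample is certain from the text: a city-wide objective, with minors and six districts ineligible and no narrowing of the claim. Its size is unknown. Under the assumed 10-30% district share and 5-point prevalence gap it is 0.5-1.5 points, in either direction, and outside the stated 2-point error.

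The missing stop at Q3 is a fact of the printed script. Its harm is conditional: if the ineligible are not removed, apparent participation falls and the imputed and model-based prevalence can be distorted by an amount the protocol does not allow one to compute. The taxi-based ratio among those swayed by the offer is largely unaffected.

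Section 3.1 and criterion 3.2.1.4 contradict each other on repeat consent. The effect is confined to people who refuse repeats in advance, and its size cannot be estimated from the protocol.

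**What to change.** - **Sections 2.1 and 5.3.1:** state the target as adults (18+) living in the included districts, and standardise or adjust to that population only.
- **Appendix 1:** add a stop after Q3 for codes 6, 8, 9, 10, 15 and 17.
- **Calls already made:** restrict the imputation and selection models to eligible respondents. District of residence is settled before the offer is made, so dropping these people leaves the randomised taxi comparison intact.
- **Section 3.2.1.4:** reconcile with Section 3.1 by applying it to the cohort part only, so that one valid sample counts towards cross-sectional prevalence.

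The cost is a few changes of wording, one script filter and one analysis restriction, with no new data. The downside is that the prevalence claim covers a narrower population than the whole city.
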